8.2 Intercurrent Event 2 (IE2): Premature Discontinuation of Study Drug

Following the intent-to-treat (ITT) principle, a treatment policy strategy will be used to handle the IE2. Data collected on/after premature discontinuation of study drug will be used for all efficacy endpoints.

The only exception is when data are collected on/after the date subjects switching to other treatments for CD, which will be handled as follows:

- **Binary endpoints:** A composite strategy will be used in the efficacy analysis: the subject will be considered as non-responder at all visits after the initiation of other CD-related treatments.
- **Continuous endpoints:** A hypothetical strategy will be used in the efficacy analysis. Data collected after the initiation of other CD-related treatments will not be used in the analysis. Efficacy analysis will be handled by using corresponding statistical models (e.g., MMRM model).

The other CD-related medications include:

- Biologics approved for CD (Adalimumab, Certolizumab, Infliximab, Ustekinumab, Vedolizumab, Natalizumab)
- Any investigational compound
- Systemic glucocorticoids and rectal glucocorticoids
- Immunomodulators

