5.3 Prohibited Medications and Therapy

Subjects must be able to safely discontinue any prohibited medications as specified in Section 5.1 and Section 5.4. Subjects must be consented for the study prior to discontinuing any prohibited medications for the purpose of meeting study eligibility.

The following medications are prohibited through the end of study drug administration:

- All biologic therapies used for the treatment of CD or with potential for additive immunosuppressive effect including but not limited to the following (including biosimilars): abatacept (Orencia®), adalimumab (Humira®), anakinra (Kineret®), belimumab (Benlysta®), certolizumab pegol (Cimzia®), etanercept (Enbrel®), golimumab (Simponi®), infliximab (Remicade®), natalizumab (Tysabri®), rituximab (Rituxan®), tocilizumab (Actemra®), ustekinumab (Stelara®), vedolizumab (Entyvio®), and risankizumab (Skyrizi®).
- Investigational agents
- All other therapies with a potential therapeutic impact on CD (except for those allowed per protocol) including but not limited to the following: Janus kinase (JAK) inhibitors such as tofacitinib, cyclosporine, tacrolimus, or mycophenolate mofetil.
- Live vaccination (see Section 5.4).
- Rectal therapy, with the exception of those required for endoscopy.
- IV, intramuscular, intra-articular, epidural, intra-bursal, intra-tendon sheath, trigger or tender point, or rectal administration of glucocorticoids;
- Super high potency and/or high potency topical glucocorticoids (see Operations Manual [Appendix F], Section 3.5). From Weeks 0 to 28 of the Maintenance Period super high potency and/or high potency topical glucocorticoids are permitted for non-CD-related adverse events.
- Corticotropin gel injection (e.g., Acthar®)
- Apheresis (e.g., adacolumn apheresis).
- Exclusive enteral nutrition or any parenteral nutrition.
- NSAIDs with the exception of low dose aspirin daily and selective COX-2 inhibitors.
- Traditional oral Chinese medicine (e.g., tripterygium glycosides, sinomenine, total glucosides of white peony).

Strong CYP3A Inhibitors

Systemic use of known strong cytochrome P450 3A (CYP3A) inhibitors (includes over-the-counter or prescription medicines, vitamins and/or herbal supplements) is not permitted from Screening through

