8.1 Intercurrent Event 1 (IE1): CD-Related Confounding Medications

The CD-related confounding medications intercurrent event is defined as follows.

In the Induction Period:

1. Initiation of protocol-defined Rescue Therapy for the Induction Period;
2. Initiation of glucocorticoids after Baseline of the Induction Period;
3. Fail to complete glucocorticoid taper by Week 6 of the Induction Period;
4. Initiation/increasing doses of aminosaliclates or immunomodulators.

In the Maintenance Period:

- Initiation of protocol-defined Rescue Therapy for the Maintenance Period.

Within each period, the time point of the CD-related confounding medications intercurrent event is defined as the date when one of the scenarios above occurs for a subject.

Binary endpoints: A composite strategy will be used in the efficacy analysis: the subject will be considered as non-responders at all visits on/after the CD-related confounding medications intercurrent event.

Continuous endpoints: A hypothetical strategy will be used in the efficacy analysis. Data collected on/after the initiation of CD-related confounding medications will not be used in the analysis. Efficacy analysis will be handled by using corresponding statistical models (e.g., the Mixed-Effect Model Repeated Measurement [MMRM] model).

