9.2.1 Categorical Endpoints

For binary efficacy endpoints, missing data will be handled using the following approaches:

- The primary approach for handling missing data in the analysis of binary endpoints will use **Non-Responder Imputation (NRI) while incorporating Multiple Imputation (MI) to handle missing data due to **CCOVID-19 (NRI-C)**.
 - The NRI-C will categorize any subject who does not have an evaluation during a pre-specified visit window (either due to missing assessment or due to early withdrawal from the study) as a non-responder for the visit. The only exception is that missing data due to COVID-19 infection or logistical restriction will be handled by MI. At each visit, subjects will be characterized as responders or non-responders based on MI imputed values if missing due to COVID-19; otherwise, subjects will be considered as non-responders for missing due to other reasons in the NRI-C approach. In addition, at and after the CD-related confounding medications intercurrent event (see Section 8.1) and on/after the date of initiation of CD-related medications after premature discontinuation of study drug (see Section 8.2) in the corresponding study period, subjects will be considered as non-responders and will not be imputed by MI.**
- A sensitivity analysis for binary endpoints will use **NR**I** with No special data handling for missing due to **CCOVID-19 (NRI-NC)**.
 - NRI-NC will be performed in the same way as NRI-C without the exception above. Missing due to COVID-19 infection or logistical**

restriction will also be counted as non-responders. Subjects on or after the occurrence of the CD-related confounding medications intercurrent event and on/after the date of initiation of CD-related medications after premature discontinuation of study drug will still be considered as non-responders.

- Details on MI method in NRI-C are described below:

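### The SAP's confounding-medication rule misses prohibited CD therapies taken while still on study drug, and its post-discontinuation list names neither risankizumab nor JAK inhibitors

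*SAP*

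**What the plan says.** **SAP 8.1.** "The CD-related confounding medications intercurrent event is defined as follows", and a list follows. For Induction it has four items: protocol-defined rescue, starting glucocorticoids, failing to finish the glucocorticoid taper by Week 6, and "Initiation/increasing doses of aminosaliclates or immunomodulators". For Maintenance there is one: "Initiation of protocol-defined Rescue Therapy for the Maintenance Period". Binary endpoints become non-response from the event onward.

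**SAP 8.2.** Data after premature discontinuation of study drug are used, and "The only exception is when data are collected on/after the date subjects switching to other treatments for CD". The medications that trigger the exception are systemic and rectal glucocorticoids, immunomodulators, any investigational compound, and "Biologics approved for CD (Adalimumab, Certolizumab, Infliximab, Ustekinumab, Vedolizumab, Natalizumab".

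**SAP 9.2.1.** The non-responder override has two medication triggers: IE1, and data "on/after the date of initiation of CD-related medications after premature discontinuation of study drug".

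**Protocol 5.3.** Prohibited through the end of study drug administration are "All biologic therapies used for the treatment of CD or with potential for additive immunosuppressive effect including but not limited to the following", with risankizumab named in the list that follows, and other therapies with potential impact on CD, such as "Janus kinase (JAK) inhibitors such as tofacitinib, cyclosporine, tacrolimus, or mycophenolate mofetil". Investigational agents are also prohibited.

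**Protocol 3.1 and 7.3.** The estimand is response without concomitant medication that could confound efficacy. Section 7.3 makes subjects non-responders after any such medication, gives its items as inclusions, and does not depend on study drug having been stopped.

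**The concern.** The SAP is narrower than the rule it has to implement. It puts the drugs most able to produce a response in CD behind a condition, prior discontinuation, that neither the estimand nor Protocol 7.3 imposes. A response produced by another CD therapy could then be credited to the randomised arm.

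No planned analysis would show this. NRI-NC changes only the handling of COVID-19 missingness. The as-observed analysis uses data after both intercurrent events, apart from data after ABBV-154 rescue. SAP Appendix A only counts subjects who took prohibited medication.

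**Working it through.** **1. Can a subject take a prohibited drug and remain on study drug?** Yes, on the text. Protocol 5.5 makes introduction of a prohibited medication a reason for immediate discontinuation only where continuing would also place the subject at risk.

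**2. How does each SAP rule treat that subject?** Suppose a biologic is started during Induction with study drug continuing.
- IE1 (SAP 8.1): not triggered, because no biologic is listed.
- IE2 exception (SAP 8.2): not triggered, because study drug has not been stopped.
- Override (SAP 9.2.1): not triggered, because it repeats the discontinuation condition.
- Result: observed data are used. If the Week 12 endoscopy meets the response definition, the subject counts as a responder on the primary endpoint.
- Protocol 7.3: non-responder, if the biologic is judged able to confound efficacy.

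An investigational agent gives the same result. So does a JAK inhibitor, unless it is classed as an immunomodulator. The supplied documents do not define that term, and Protocol 5.3 lists JAK inhibitors by name.

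**3. Is the 8.2 list current?** It names six biologics and not risankizumab. Protocol 5.3 names risankizumab in the version whose synopsis is dated 20 December 2022. SAP 2.0 is dated 10 February 2023, and its version history records a revision of Section 8.2. JAK inhibitors are not named either. Cyclosporine, tacrolimus and mycophenolate are covered only if they count as immunomodulators.

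**4. Which endpoints does each gap reach?** Protocol 5.6 removes endoscopy from the assessments continued after study drug is stopped, so a missing Week 12 or Week 40 endoscopy is normally set to non-response. The list gap therefore bears mainly on CDAI and SF/AP remission. The on-drug gap reaches all binary endpoints, including the primary.

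**5. Maintenance.** SAP 8.1 counts rescue only. SAP Table 2 labels the same event as initiation or dose escalation of confounding medication. Protocol 5.4 bars changes to oral glucocorticoids, aminosalicylates and immunomodulators only after Week 28 of that period. The definition and the label do not match.

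**6. Scale.** The plan's own power comes first (Protocol 7.10, SAP 2.4). Inputs: placebo 11%, difference 26 points (so active 37%), two-sided alpha 0.10 (z = 1.645), and 53 or 40 per group. With p̄ the mean of the two rates,

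power = Φ{[Δ√n − z√(2p̄(1−p̄))] / √(p₁(1−p₁)+p₂(1−p₂))}.

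- n = 53: (0.26 × 7.280 − 1.645 × 0.604) / 0.575 = 1.56, power 94.1%. The plan says more than 90%; reproduced.
- n = 40: (0.26 × 6.325 − 1.645 × 0.604) / 0.575 = 1.13, power 87.1%. The plan says more than 80%; reproduced.

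Now assume that m placebo subjects respond solely because of an uncaptured drug, so the placebo rate is 0.11 + m/n. Each removes 100/53 = 1.9 points or 100/40 = 2.5 points.

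| m | Difference, n = 53 | Power | Difference, n = 40 | Power |
|---|---|---|---|---|
| 0 | 26.0 | 94.1% | 26.0 | 87.1% |
| 1 | 24.1 | 89.9% | 23.5 | 78.9% |
| 2 | 22.2 | 84.1% | 21.0 | 69.1% |
| 3 | 20.3 | 77.0% | 18.5 | 58.2% |
| 5 | 16.6 | 59.6% | 13.5 | 36.9% |

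The values of m are assumptions. The same subjects in an active arm would raise the difference by 1.9 or 2.5 points each.

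**The case against.** The strongest reply is that the intent is already clear and cases will be rare. Protocol 7.3 states the wide rule. SAP 8.2 speaks generally of other treatments for CD, introduces its list with the word *include*, and Tables 1 and 2 use general labels. A JAK inhibitor taken for CD after stopping could be caught without being named. On-drug use is a protocol deviation. A Maintenance subject who receives ABBV-154 rescue is a non-responder at all later visits, so any later drug use by that subject cannot matter.

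Much of this stands. It softens the list gap to an ambiguity and makes large numbers unlikely. It does not close the on-drug gap: IE1 is given as a definition, and the discontinuation condition is explicit in SAP 9.2.1.

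A reader might also infer more than the documents support:
- *That aminosalicylates escape after discontinuation in Induction.* They do not. The IE1 item on starting or increasing them applies on or off study drug, and Protocol 5.3 does not prohibit them.
- *That the treatment difference is biased towards no effect by a known amount.* No usage rate or imbalance between arms is given, and use in an active arm works the other way.
- *That any such subject is necessarily a responder.* The subject can be counted as one, if the response criteria are met.

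**Conclusion.** The point holds as a mismatch between the SAP's operative rules and the estimand. The on-drug gap is clear from the text and reaches the primary endpoint. The omission of risankizumab and JAK inhibitors from the 8.2 list is real but secondary: the list can be read as open, and it bears mainly on CDAI and SF/AP remission.

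Neither the size nor the direction of any bias can be established from the documents. The 1.9 and 2.5 points per subject are simple arithmetic on the planned group sizes. The number of such subjects, and the premise that each responds only because of the other drug, are assumptions. The planned sample size and power figures are sound and are not in question. With arms this small a few cases would matter, so the rule should be settled before unblinding.

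**What to change.** Keep every existing IE1 item, including rescue and failed taper, and amend the SAP as follows.

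- **Sections 8.1, 8.2 and 9.2.1, binary endpoints:** initiation after Baseline of any CD therapy prohibited in Protocol 5.3 makes the subject a non-responder from that date, whether or not study drug has been stopped. Name risankizumab and other biologics, JAK inhibitors, cyclosporine, tacrolimus, mycophenolate and investigational agents. Tie the rule to initiation, so that oral glucocorticoids permitted at Baseline are not flagged.
- **Continuous endpoints:** apply the existing hypothetical strategy from the same date.
- **Immunomodulators:** define the term.
- **Maintenance:** reconcile the rescue-only definition in 8.1 with the Table 2 label and with Protocol 7.3. The addition above should not by itself turn background-medication changes that are not barred before Week 28 into failures; how those are handled needs an explicit statement.
- **Classification:** have blinded staff classify individual cases before unblinding for the analysis concerned.

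The cost is SAP wording, an updated medication code list and a blinded review. No new data are collected, and the sample size does not change.

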9.0 Efficacy Analyses

9.1 General Considerations

All efficacy analyses will be conducted in the ITT Populations in each period. All tests will be 2-sided at an alpha level of 0.1.

For all efficacy endpoints, the descriptive statistics will be provided by treatment group for each of the study period. The statistics include number of observations, mean, standard deviation, 95% CI, minimum, median, and maximum for continuous variables, and number, percent and two-sided 95% CI for discrete variables. And number of subjects with missing data due to COVID-19 pandemic will be summarized for primary and secondary efficacy endpoints.

Unless otherwise specified, any subject will be analyzed according to the actual stratum the subject belongs to.

The Primary Analysis for the Induction Period and Re-Induction Period will be performed after all subjects have completed Week 12 of the Induction Period and Re-Induction Period, respectively, or prematurely discontinued study participation. This is the final efficacy analysis for the Induction Period and Re-Induction Period, respectively.

The final analysis will be conducted after all subjects have completed Week 40 of the Maintenance Period plus the 70 day Follow-up Visit or prematurely discontinued study participation. This is the final efficacy analysis for the Maintenance Period. To ensure the

integrity of the trial, the study sites and subjects will remain blinded until the final database lock is completed.

In Section 9.0, "Baseline" refers to the last non-missing observation prior to the first administration of study drug in the Induction Period, unless specified otherwise. "Comparison of treatment groups" refers to (i) comparison of each ABBV-154 group and placebo group in the Induction Period; (ii) comparison of Re-Induction Group 2 and Re-Induction Group 1 in the Re-Induction Period; (iii) comparison of each ABBV-154 group and placebo group for the randomized portion in the Maintenance Period.

"Stratification factors for the corresponding period" refers to randomization stratification factors specified in Section 2.3 except for the Maintenance Period, the randomization stratification factors used in efficacy analyses for the Maintenance Period are

- Achievement of CR100 at entry of the Maintenance Period (Week 12 of the Induction/Re-Induction Period): Yes vs No;
- Entry to the Maintenance Period: Induction Period vs Re-Induction Period.

For the comparison between ABBV-154 80 mg SC EOW and Placebo in the Maintenance Period, all data from subjects of the corresponding ITT3/ITT3-RN population will be included.

For the comparison between ABBV-154 230 mg SC EOW and Placebo in the Maintenance Period, data from subjects of the corresponding ITT3/ITT3-RN population will be included with the exception that data from subjects who are randomized to Induction Group 1 (ABBV-154 150 mg IV + 80 mg SC EOW), considered as responder at Week 12 of the Induction Period and entered the Maintenance Period will not be included.

Analysis of Categorical Variables:

For categorical variables, frequencies and percentages will be reported for each treatment group in each of the study period. In each period, comparison of treatment groups will be performed using the Cochran Mantel-Haenszel (CMH) test adjusting for stratification

factors for the corresponding period. If there is a stratum that has no subject in it, a value of 0.1 will be added to the denominator to the corresponding stratum in order to prevent dividing by 0, as suggested in Greenland and Robins (1985).¹ Point estimates and 95% confidence intervals (CI) for the difference in proportions between treatment groups will be provided. Construction of CI for the common risk difference will be based on the Mantel-Haenszel estimate adjusting for stratification factors for the corresponding study period.

Analysis of Continuous Variables:

For continuous variables, the model based mean and standard error will be provided. The mean value of the variable at baseline and each scheduled visit will also be presented for each treatment group. Continuous variables collected longitudinally will be using a Mixed-Effect Model Repeated Measurement (MMRM) model. Continuous efficacy variables which are collected at only one post-baseline visit (such as SES-CD) will be analyzed using an Analysis of Covariance (ANCOVA) model. Point estimates and 95% CIs of mean change from baseline within each treatment group, and the difference between treatment groups for each period will be provided.

9.2 Handling of Missing Data

Missing data could occur due to various reasons, including missing visits/assessments, early withdrawal from the clinical trials, or missing due to COVID-19 infection or logistic restrictions during the pandemic. Assessments on or after any intercurrent event will be handled as specified in Section 8.0.

The COVID-19 pandemic is interfering with the conduct of many ongoing trials, with potential impacts on treatment duration and the collection, analysis, and the interpretation of clinical trial data. For example, some scheduled visits may be missed due to self-quarantine or local government restrictions on travel; some visits may also be delayed or canceled due to healthcare resource constraints during the pandemic. Impacted visits due to COVID-19 will be recorded in the database. The probability of having missed

visits and missing data due to COVID-19 infection or logistical restrictions related to the COVID-19 pandemic can be reasonably assumed to be unrelated to the unobserved values. Therefore, for the purpose of statistical analysis, it is reasonable to assume that these missing data are missing at random (MAR) and the statistical models that require MAR assumption are appropriate. The intent is to provide reliable estimates of the treatment effects under the scenario without the impact of COVID-19 pandemic.

Missing data for the efficacy analyses will be handled using the methods described below.

9.2.1 Categorical Endpoints

For binary efficacy endpoints, missing data will be handled using the following approaches:

- The primary approach for handling missing data in the analysis of binary endpoints will use **Non-Responder Imputation (NRI) while incorporating Multiple Imputation (MI) to handle missing data due to **CCOVID-19 (NRI-C)**.
 - The NRI-C will categorize any subject who does not have an evaluation during a pre-specified visit window (either due to missing assessment or due to early withdrawal from the study) as a non-responder for the visit. The only exception is that missing data due to COVID-19 infection or logistical restriction will be handled by MI. At each visit, subjects will be characterized as responders or non-responders based on MI imputed values if missing due to COVID-19; otherwise, subjects will be considered as non-responders for missing due to other reasons in the NRI-C approach. In addition, at and after the CD-related confounding medications intercurrent event (see Section 8.1) and on/after the date of initiation of CD-related medications after premature discontinuation of study drug (see Section 8.2) in the corresponding study period, subjects will be considered as non-responders and will not be imputed by MI.**
- A sensitivity analysis for binary endpoints will use **NR**I** with No special data handling for missing due to **CCOVID-19 (NRI-NC)**.
 - NRI-NC will be performed in the same way as NRI-C without the exception above. Missing due to COVID-19 infection or logistical**

restriction will also be counted as non-responders. Subjects on or after the occurrence of the CD-related confounding medications intercurrent event and on/after the date of initiation of CD-related medications after premature discontinuation of study drug will still be considered as non-responders.

- Details on MI method in NRI-C are described below:
 - Markov Chain Monte Carlo (MCMC) will be first applied to augment data into monotonic missing pattern (where applicable) and PROC MI will be used to generate 30 datasets using the regression method. If the binary endpoints are derived from the continuous variables, PROC MI will be applied to the continuous variables. The variables to be included in the imputation model are: treatment group, randomization stratification factors for the corresponding period, age, gender, weight, baseline measurement (if applicable) and post-baseline measurements at each visit for the respective analysis period up to the end of the analysis period. The random seed for MCMC and the random seed for PROC MI are specified in [Appendix E](#). The imputed post-baseline measurements will be rounded to the same precision as the observed data before the determination of responder status. Subjects will be characterized as responders or non-responders based on MI imputed data. Using the CMH model adjusted by randomization stratification factors, the endpoints will be analyzed using each of the 30 imputed datasets. SAS PROC MIANALYZE will be used to generate the final inferences of the risk difference between treatment groups, using Rubin's rule.² Note that measurements will be set to missing 1) at or after the occurrence of the CD-related confounding medications intercurrent event, or 2) on/after the date of initiation of CD-related medications after premature discontinuation of study drug before applying MI. After the MI imputation, an NRI override will be implemented for missing values 1) missing values due to reasons other than COVID-19 infection or logistic reasons, or 2) at or after the occurrence of the CD-related confounding medications or 3) on/after the date of initiation of CD-related medications after premature discontinuation of study drug, that is, regardless of MI imputed values, subjects satisfying 1) or 2) or 3) will be considered as "non-responder" for binary efficacy endpoints.

